### **Exclusion criteria (for both able-bodied and SCI groups)**

Clinical signs or symptoms of heart disease, hypertension, coronary disease, diabetes, other neurological disease, cancer, recent weight change >15 pounds, abnormal resting ECG, pregnant and/or breastfeeding women, underweight and obese individuals (body mass index between 18.5 and 29.9), use of amphetamines (Ritalin, Adderall, Concerta) in the past 48 hours, tibial fracture or tibial stress fracture in the past year.

In addition, those with SCI will have no extreme spasticity to avoid spontaneous contractions and cannot be on baclofen due to its potential autonomic effects.

## IV. SUBJECT ENROLLMENT

In the past, we have successfully recruited young males and females by posting flyers on college campuses and/or by posting on internet websites. The website ad has a short description of the project and a number to contact if they would like more information. When the potential subject

## PARTNERS HUMAN RESEARCH COMMITTEE DETAILED PROTOCOL

makes contact with the study staff, we use a phone screening of health questions and a short description of the study. This process usually takes 15 to 20 minutes. If individuals meet eligibility requirements from the phone screening and are interested in participating, they are then scheduled for a physical screening. At that time, we mail a consent form to give opportunity to read and understand the specifics of the study.

We will recruit SCI participants from the outpatient therapy department and the Exercise for Persons with Disabilities (ExPD) program at Spaulding Rehabilitation Network. Flyers will be posted at SRH outpatient sites and/or given to potential subjects along with a phone number to call if they are interested in learning more about the study. Our laboratory has been regularly enrolling SCI patients for research from the SRN. For the able-bodied participants, in the past, we have successfully recruited young males and females by posting flyers on college campuses and/or by posting on internet websites. The website ad has a short description of the project and a number to contact if they would like more information. When the potential subject makes contact with the study staff, we use a phone screening of health questions and a short description of the study. This process usually takes 15 to 20 minutes. If individuals meet eligibility requirements from the phone screening and are interested in participating, they are then scheduled for a physical screening. At that time, we mail a consent form to give opportunity to read and understand the specifics of the study.

Research study staff will obtain volunteer consent in accordance with guidelines established by the Institutional Review Board during the study visit to the Cardiovascular Laboratory. Participants are encouraged to ask questions and are reminded that participation is strictly voluntary and will not affect their current or future care at Spaulding Rehabilitation Hospital or any of its affiliates.

### **V. STUDY PROCEDURES**

#### **Study Visit**

Once recruited for the study, the volunteers will visit the laboratory for a health screening session to further determine eligibility. This 30-minute screening session includes obtaining informed consent, health history, and obtaining height and weight measurements.

Once volunteers complete the screening process and meet the study inclusion criteria they will continue the visit to investigate the effect of sympathetic outflow to tibial perfusion. The study visit will take approximately 3.5 hours to complete. The screening visit and the study visit may occur on the same day or on different days.

#### **Detailed procedures**

Throughout the protocol, able-bodied volunteers will be fully instrumented for measurements of tibial blood flow, muscle/bone sympathetic activity, popliteal blood flow velocity, ECG, beat-by-beat arterial pressure, brachial arterial pressure, and respiration (see Measurements below). All those with SCI enrolled in this study will have complete injuries and thus vascular sympathetic control is disrupted below the level of injury. Hence, in individuals with SCI the arterial network in bone might act as a simple pressure passive system. Given the disrupted vascular sympathetic control, in those with SCI we will not record muscle/bone sympathetic activity.

In able-bodied, we will use direct microneurographic measures of nervous activity to the lower leg vasculature in the common peroneal nerve as a measure of sympathetic activity to the bone

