## III. SUBJECT SELECTION

### **Inclusion criteria**

It is anticipated that 34 healthy males and 34 healthy females aged 18 to 40 years will be recruited and enrolled for this study.

Also, we anticipate we will recruit 17 males with SCI, aged 18 to 40 years, with injuries American Spinal Injury Association Impairment Scale (AIS) A and B and C, with full hand function. We will only enroll males with SCI since the SCI population is predominantly male (about 75%).

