## PARTNERS HUMAN RESEARCH COMMITTEE DETAILED PROTOCOL

vasculature of the tibia throughout the protocol. Our assumption is that peroneal nerve sympathetic activity reflects vasomotor output to both muscle and bone of the lower leg. Though this assumption is not testable prior to having data in hand, we assume that Hilton's law prevails. According to Hilton's law, bone innervation derives from the peripheral nerves of the muscle that overlies the bone. The common peroneal nerve primarily innervates the fibula, but also the deep peroneal branch innervates the tibialis anterior which overlies the tibia. Though we acknowledge this is potentially inexact, our sympathetic nervous activity measure should broadly reflect sympathetic outflow to the lower leg.

We will use three approaches to increase sympathetic outflow to the leg vasculature: head tilt, cold pressor test, and isometric handgrip exercise (IHE) to fatigue. In those with SCI, we expect that bone vasculature will respond as a pressure passive system.

Subjects will lie supine throughout the study protocol. After instrumentation, the subject will perform three maximal voluntary contractions (MVC) on a handgrip dynamometer. This is to determine 30% MVC for sustained isometric exercise. Afterwards, an adequate nerve recording will be obtained. To ensure that a good nerve recording is obtained, the subjects will be asked to perform a Valsalva maneuver, which results in an expected increase in sympathetic activity. Invented by Antonio Maria Valsalva in the 17th century, the Valsalva maneuver, a prolonged expiration against a closed glottis, is widely used because of its safety and ease of quantification. This voluntary act of straining creates transient changes in intra-thoracic and intra-abdominal pressure with concomitant increases in sympathetic activity. To achieve this, subjects will be asked to breathe through a tube with a small vent in the glottis to prevent them from increasing mouth instead of chest pressure. A pressure gauge attached to this tube will allow the subject maintain a target pressure of 40 mmHg for 15 seconds. Data will be obtained for 1 minute prior to the maneuver, 1 minute after, with 2 minutes of recovery.

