*Sympathetic Microneurography.* Multiunit, post-ganglionic muscle sympathetic nerve activity will be recorded with a tungsten microelectrode in the peroneal nerve only in the able-bodied population. The peroneal nerve will be mapped at the fibular head via low voltage transcutaneous electrical stimuli. Subsequently, the microelectrode is inserted manually through the unanesthetized skin and initially provides low voltage electrical stimuli (1-4 volts) to help locate the nerve. When the microelectrode enters a nerve fascicle innervating muscle, involuntary twitches are induced. The microelectrode is then used to record sympathetic efferent nerve outflow to calf muscle. This procedure is safe and the principal investigator has performed over 1000 experiments since 1991 without complication. The raw nerve signal will be amplified, rectified and integrated for visual inspection during experiments (Nerve Traffic Analyzer, Model 662c-3, University of Iowa Bioengineering, Iowa City, IA) and the amplified raw signal will be directly sampled at 20 kHz for further signal processing.

*Beat-by-Beat Calf Blood Flow.* We will use Doppler derived flow velocities to estimate whole limb blood flow through the popliteal artery. A continuous wave 4 MHZ Doppler probe (Multidop T2, DWL) is placed against the skin under the knee to isolate the popliteal artery proximal to the bifurcation.

*Electrocardiogram.* A standard 4-lead electrocardiogram will be used to obtain continuous heart rate.

*Arterial Pressure.* The arterial waveform in a finger of the hand will be derived on a beat-to-beat basis by the Finapres Blood Pressure System (Finapres, Ohmeda) with brachial oscillometric blood pressure (Dash 2000, GE) as a standard measure of arterial pressure.

*Respiration.* A respiratory belt will be placed around the chest for breathing depth and frequency. This signal does not provide exact tidal volumes and will only be used to monitor breathing.

Following the removal of instruments, the able-bodied volunteers will be asked to complete the online MSNA questionnaire administered via REDCap, if the patient had the electrode placed

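### The second protocol admits AIS A, B and C injuries but states that every SCI participant will have a complete injury, and omits nerve recording in SCI on that ground

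*Combined protocol and SAP*

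**What the plan says.** The combined document holds two protocols. This point concerns the second, on sympathetic activity and tibial perfusion.

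- **Entry** (III, Inclusion criteria): 17 men with SCI, "with injuries American Spinal Injury Association Impairment Scale (AIS) A and B and C, with full hand function".
- **Exclusion** (III, Exclusion criteria): beyond the exclusions shared with able-bodied volunteers, "those with SCI will have no extreme spasticity to avoid spontaneous contractions and cannot be on baclofen due to its potential autonomic effects". Incomplete injury is not excluded.
- **Premise** (V, Detailed procedures): "All those with SCI enrolled in this study will have complete injuries and thus vascular sympathetic control is disrupted below the level of injury".
- **Decision drawn from it** (same paragraph): "Given the disrupted vascular sympathetic control, in those with SCI we will not record muscle/bone sympathetic activity". The Measurements section agrees: "Multiunit, post-ganglionic muscle sympathetic nerve activity will be recorded with a tungsten microelectrode in the peroneal nerve only in the able-bodied population".
- **Later use** (V, the part on sympathetic outflow with raised systemic pressure): the closing paragraph on SCI starts from a lack of sympathetic control, and hence no rise in outflow during tilt, cold pressor or handgrip.
- **Expected response**: worded with caution. Detailed procedures say that "in individuals with SCI the arterial network in bone might act as a simple pressure passive system", and further on "In those with SCI, we expect that bone vasculature will respond as a pressure passive system".
- **Analyses** (end of V; VI, Statistics): in SCI, tibial perfusion is related to popliteal flow and to mean arterial pressure. Aim 3 compares able-bodied volunteers with SCI. No planned analysis uses AIS grade or lesion level.

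**The concern.** A site that follows the inclusion criteria may enrol grade B and C injuries. The procedures then treat everyone enrolled as having a complete injury, and two things rest on that: the decision not to record nerve activity in SCI, and the statement that outflow will not rise during the manoeuvres.

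If some eligible B or C participants keep sympathetic control to the leg, the SCI relations of perfusion to pressure and to popliteal flow would pool two kinds of response. The Aim 3 contrast would then compare able-bodied volunteers with a mixed group. No direct measurement in SCI would show that this had happened, and no planned analysis would separate the grades.

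**Working it through.** No formula or power figure is involved. The check is whether the statements can hold together, and what can be said about size.

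1. **Does anything narrow the entry criterion to complete injuries?** The inclusion criteria name three grades. The SCI-specific exclusions are extreme spasticity and baclofen. The Statistics section has no restriction by grade. Nothing narrows it.

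2. **Could complete be read so that all three grades fit?** The documents do not define the grades. I take the usual meaning of the scale, in which A is complete and B and C are incomplete. A looser sense, motor-complete, might take in B but not C, so the conflict remains on either reading. The companion protocol gives some support from within the document. Its inclusion criteria list the same three grades and then restrict its aim 2 to complete injuries, so the term is used there as narrower than A, B and C together. This is support only: it is a separate protocol, and its Specific Aims and its loading procedures describe that subset by time since injury alone.

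3. **What hangs on the premise?** The reasoning in Detailed procedures is a chain: complete injury, therefore disrupted control below the lesion, therefore no nerve recording. The later paragraph goes from disrupted control to lack of control. If the first link fails for some participants, the stated ground for the rest fails for them too.

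4. **How many could be affected?** With 17 planned SCI participants (VI, Sample Size) and an unknown share f with grade B or C, the count is 17 × f. The entry criterion allows any f from 0 to 1:
   - f = 0 gives 17 × 0 = 0
   - f = 1 gives 17 × 1 = 17

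   The range is 0 to 17 of 17. The share of those who keep control to the leg is also not given, so no attenuation, bias or power figure can be derived.

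5. **Does lesion level matter as well?** Detailed procedures place the loss of control below the lesion, while the inclusion criteria set no level beyond requiring full hand function. Grade alone therefore does not fully describe what the premise needs.

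6. **Could the trial's own data settle the premise afterwards?** Not cleanly. The companion protocol (Background; leg dependency procedures) says that lowering the leg raises transmural pressure and engages myogenic vasoconstriction, a local mechanism, and cites larger falls in flow in SCI. Head-up tilt also lowers the leg relative to the heart, so perfusion could fall with no sympathetic control at all. A rise in arterial pressure during cold pressor or handgrip also raises transmural pressure, so perfusion that fails to follow pressure is open to the same explanation. The perfusion measure is a percent change in total hemoglobin content, not flow itself.

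**The case against.** The strongest reply is that this is a loose sentence with little behind it. The pressure-passive response is only a hypothesis. The SCI analyses merely relate perfusion to pressure and to popliteal flow and do not impose absence of control. Disrupted control need not be false for a grade B or C injury. Nothing in the documents shows that such participants keep control to the leg.

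Much of this stands, and it limits the point:

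- A reader might infer that the pressure-passive expectation is itself the error. It is not; it is worded as something that might occur or is expected. What is stated as fact is completeness, and later the lack of control.
- A reader might infer that Aim 3 is diluted or underpowered. The documents do not support that. Aim 3 is not worded as a contrast of present against absent sympathetic control, and the Background presents SCI as a model of reduced loading as well as of sympathetic loss. That model description does not conflict with the entry criterion.
- A reader might infer from the screening list that AIS grade would not be known. The list says only what the session includes, and grade must be known to apply the entry criterion.
- A reader might propose the tilt or pressor responses as a test of the premise. The myogenic mechanism rules that out. Those responses, and popliteal flow against pressure, are indirect and non-specific evidence.

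The reply does not remove the contradiction. The protocol gives completeness as its reason for not measuring nerve activity in SCI, and its own entry rule does not secure completeness.

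**Conclusion.** The inclusion criteria and the completeness statement in Detailed procedures contradict each other in current text, and the later statement of lack of control inherits the problem. That much is certain, given the usual meaning of the AIS grades.

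The consequences are conditional. They require that B or C participants are enrolled and that some keep sympathetic control to the leg. If both hold, the SCI analyses and the Aim 3 comparison could mix different responses without a direct measure to reveal it. No effect size, bias or power loss is claimed. This should be corrected because the text cannot be followed as written and the correction is cheap, not because harm has been shown.

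**What to change.** Reconcile three places in the second protocol: the inclusion criteria, the completeness statement in Detailed procedures, and the later paragraph that takes lack of sympathetic control as given. The documents do not settle which is intended, so the sponsor must decide whether the entry criterion or the premise changes.

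If B and C remain eligible:

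- Reword the two procedural statements so that loss of sympathetic control to the leg is an assumption.
- Carry AIS grade and lesion level into the analysis data.
- Report the SCI analyses (perfusion against mean arterial pressure, and against popliteal flow) and the Aim 3 comparison in all SCI participants and, as a sensitivity analysis, in complete injuries only.
- Describe perfusion and popliteal flow responses to pressure only as indirect, non-specific evidence on the assumption. Do not set a rule that a fall on tilt, or perfusion not following pressure, refutes it.

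Cost: wording changes and, if B and C stay, two variables in the dataset, of which grade must already be known at entry. If B and C are enrolled, the complete-injury subset will be smaller than the SCI group and its estimates less precise. If the entry criterion is the text that changes, the recruitment pool narrows.

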## PARTNERS HUMAN RESEARCH COMMITTEE DETAILED PROTOCOL

vasculature of the tibia throughout the protocol. Our assumption is that peroneal nerve sympathetic activity reflects vasomotor output to both muscle and bone of the lower leg. Though this assumption is not testable prior to having data in hand, we assume that Hilton's law prevails. According to Hilton's law, bone innervation derives from the peripheral nerves of the muscle that overlies the bone. The common peroneal nerve primarily innervates the fibula, but also the deep peroneal branch innervates the tibialis anterior which overlies the tibia. Though we acknowledge this is potentially inexact, our sympathetic nervous activity measure should broadly reflect sympathetic outflow to the lower leg.

We will use three approaches to increase sympathetic outflow to the leg vasculature: head tilt, cold pressor test, and isometric handgrip exercise (IHE) to fatigue. In those with SCI, we expect that bone vasculature will respond as a pressure passive system.

Subjects will lie supine throughout the study protocol. After instrumentation, the subject will perform three maximal voluntary contractions (MVC) on a handgrip dynamometer. This is to determine 30% MVC for sustained isometric exercise. Afterwards, an adequate nerve recording will be obtained. To ensure that a good nerve recording is obtained, the subjects will be asked to perform a Valsalva maneuver, which results in an expected increase in sympathetic activity. Invented by Antonio Maria Valsalva in the 17th century, the Valsalva maneuver, a prolonged expiration against a closed glottis, is widely used because of its safety and ease of quantification. This voluntary act of straining creates transient changes in intra-thoracic and intra-abdominal pressure with concomitant increases in sympathetic activity. To achieve this, subjects will be asked to breathe through a tube with a small vent in the glottis to prevent them from increasing mouth instead of chest pressure. A pressure gauge attached to this tube will allow the subject maintain a target pressure of 40 mmHg for 15 seconds. Data will be obtained for 1 minute prior to the maneuver, 1 minute after, with 2 minutes of recovery.

### *Assessing tibial perfusion in response to increased sympathetic outflow with maintained blood pressure*

This approach will provide insight to the relation between moment-by-moment bone perfusion and beat-by-beat increases in vascular sympathetic activity without alterations in systemic pressure. During head-up tilt, decreases in central blood volume and circulatory adjustments are proportional to the angle of the head-up tilt [20]. Sympathetic activity increases and muscle blood flow decreases significantly by a tilt angle of 30 degrees [21]. In addition, head-down tilt to 6-8 deg results in a decrease in sympathetic activity [22]. Hence, increased levels of head-up tilt provide a strong stimulus for active vasoconstriction in the leg, while maintaining system pressure constant. This provides a stimulus that progressively increases sympathetic activity with a maintained systemic perfusion pressure. Data will be obtained for a 5 minutes resting baseline, followed by 25 minutes of continuous tilt of successive 5 minutes periods at 10 deg head-down tilt, 0 deg tilt, 10 deg head-up tilt, and 20 deg head-up tilt.

### *Assessing tibial perfusion in response to increased sympathetic outflow and increased systemic pressure.*

The purpose of this approach is to provide insight to the relation between bone perfusion and progressive increases in sympathetic outflow accompanied by increases in systemic pressure.

## PARTNERS HUMAN RESEARCH COMMITTEE DETAILED PROTOCOL

Cold pressor test and sustained isometric handgrip will be used to increase sympathetic nervous activity, with increased systemic pressure.

The cold pressor test provokes a nociceptive response that causes increases in sympathetic activity, blood pressure, and heart rate [23]. Past work showed that these responses are water temperature dependent. Graded increases in sympathetic activity, accompanied by parallel increase in arterial pressure, were seen during immersion at 0 and 7°C, but not at 14°C [24].

A 5 minutes resting baseline will be obtained prior to the subject performing the cold pressor test. Afterwards, participants will undergo a cold pressor task, consisting of immersion of a hand for 3 min in 0°C water. This will be followed by 3 minutes of recovery data collection.

Isometric handgrip to fatigue (IHE) results in time-dependent, progressive increases in peroneal nerve sympathetic outflow and blood pressure [25]. With sustained handgrip forces greater than 25% of maximal voluntary contraction, sympathetic activity increases progressively to end exercise. Hence, IHE provides a strong stimulus for active vasoconstriction in the leg that contributes to the exercise pressor response.

A 5 minutes resting baseline will be obtained prior to the subject performing IHE at 30% MVC sustained to fatigue. An oscilloscope will be calibrated to provide the subject visual feedback on force generation; subjects will be verbally encouraged to maintain force throughout; fatigue will be determined by the investigators as maximal perceived rating of exertion accompanied by inability to maintain target force for more than 3 sec, despite continued effort.

In those with SCI, given the lack of vascular sympathetic control and thus no increase in sympathetic outflow during tilt, cold pressure, and isometric handgrip exercise, we expect that bone blood flow will respond as a pressure passive system and hence will track blood pressure response.

In able-bodied, tibial blood perfusion, an adequate nerve recording, and popliteal flow will be obtained. These time series will allow derivation of relations between nerve activity and tibial perfusion, and between nerve activity and popliteal flow. Nerve activity will serve as an index of vasoconstriction activity to the entire leg, while tibial perfusion and popliteal flow will represent a measure of downstream leg vascular responses. If nerve activity is not obtained, the subjects will still perform the procedures described above. In that case, the relationship between tibial blood perfusion and popliteal flow will be assessed.

In those with SCI, tibial blood perfusion and popliteal flow will be obtained. The relationship between tibial blood perfusion and popliteal flow will be assessed. These approaches will provide insight to the proportionality between sympathetic outflow and bone blood flow, as well as the hypothesized pressure passive bone vasculature in those with SCI.

Subjects may be asked to repeat any of the study assessments if there is difficulty obtaining results that meet our quality standards or there are equipment issues that arise.

